### 7.8 . Definition of End of Study

The end of study recruitment will be 3 months from the start date. Follow-up data will be collected for a further two weeks. Any patient remaining at that time will be given an outcome questionnaire, and will have their length of stay and other data will be censored at that point (i.e. it will be handled as the date of discharge); the fact of censoring will be noted.

### 8. INTERVENTIONS

One pack containing an eye mask and earplugs. Supplier: Delmore LTD. It will be kept in a patient labelled clear plastic pouch. It will contain minimal instructions on their use. Patients will be allowed to take them home when they leave.

#### 9. SAFETY REPORTING

### 9.1. Definition of Serious Adverse Events

Clinical Research Protocol Template version 10.0 CONFIDENTIAL © Copyright: The University of Oxford and Oxford University Hospitals NHS Foundation Trust 2015 Page 10 of 15 A serious adverse event is any untoward medical occurrence that:

- results in death
- is life-threatening
- requires inpatient hospitalisation or prolongation of existing hospitalisation
- results in persistent or significant disability/incapacity
- consists of a congenital anomaly or birth defect.

Other 'important medical events' may also be considered serious if they jeopardise the participant or require an intervention to prevent one of the above consequences.

NOTE: The term "life-threatening" in the definition of "serious" refers to an event in which the participant was at risk of death at the time of the event; it does not refer to an event which hypothetically might have caused death if it were more severe.

It is anticipated that patients will experience many events. With the exception of falls and deaths these will **not** be recorded because the likelihood of the intervention causing serious harm is considered very small, and collecting the data would be excessively burdensome and unjustified.

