#### Risks to participants

1) Allergies: Risk of patient or staff having an allergic reaction to the product.

Likelihood: 1/5 Remote Severity: 4/5 Severe Total risk score: 4/25 low risk Mitigate risk by choosing earplugs and eye masks made from hypoallergenic materials, manufactured in quality plant approved with the CE mark. Earplugs and eye masks themselves or the literature provided with them will describe their composition/materials and they will only be provided to patients with the mental capacity to use them safely in an informed manner (similar to use on an aircraft).

- Swallow/Choking risk: Risk of patients swallowing, breathing in and/or choking on earplugs. Likelihood: 1/5 Unlikely Severity: 4/5 Moderate risk Total risk score: 4/25 low risk Mitigate risk by restricting earplugs and eye masks to patient over 18 years old with capacity and awareness/ability to learning from information leaflets of how to use ear plugs/eye masks.
- 3) Infection risk: Risk of spreading infections from one patient to another and of increasing risk of patients getting otitis externa (outer ear infections). Likelihood: 3/5 Possible
   Severity: 2/5 minor
   Total risk score: 6/25 Low risk
   Mitigate risk by advising patients with ear infections not to use earplugs. Have earplugs and eye masks as single patient use (for disposal on discharge) and replace earplugs and eye masks if soiled or contaminated.
- Pressure sores: Risk of earplugs and eye masks causing a pressure ulcer if left in the bed. Likelihood: 1/5 Remote Severity: 3/5 moderate Total risk score: 3/25 Low risk Mitigate risks by good nursing practice of checking the bed for anything lost on top of the mattress, making the bed daily and frequently turning patients with high risk of pressure ulcers, as well as pressure reducing mattresses and pressure removal from damaged sites.
- 5) Increased confusion/risk of falls: increased confusion as patients forget to remove ear plugs and or eye masks and attempt to walk with ear plugs/eye masks still in place. NB/There is no evidence that this occurs, but it is conceivable that it could. Likelihood: 2/5 unlikely Severity: 3/5 moderate Total risk score: 6/25 Low risk Mitigate risk by never applying earplugs and eye masks to a patient without their express and informed request. Removing/not supplying ear plugs/eye masks to confused/confused patients who do not have mental capacity to use the aids.

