#### 9.2. Reporting Procedures for Serious Adverse Events

A serious adverse event (SAE) occurring to a participant should be reported to the REC that gave a favourable opinion of the study where in the opinion of the Chief Investigator the event was 'related' (resulted from administration of any of the research procedures) and 'unexpected' in relation to those procedures. Reports of related and unexpected SAEs should be submitted within 15 working days of the Chief Investigator becoming aware of the event, using the HRA report of serious adverse event form (see HRA website).

All SAEs (other than those defined in the protocol as not requiring reporting) must be reported on the Oxford University Hospitals NHS Trust SAE reporting form to OUH study team within 24 hours of the Site Study Team becoming aware of the event by email or fax.

In the unlikely event that a Serious Adverse Event is identified, it will be reported to the R&D office immediately. SAE reports should be faxed or emailed to: [name] or [contact]

All SAE information must be recorded on an SAE form and faxed, or scanned and emailed, to R&D. Additional and further requested information (follow-up or corrections to the original case) will be detailed on a new SAE Report Form and faxed/emailed to R&D.

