# **10.1.** Description of Statistical Methods

There will be no interim analysis.

The primary analyses will be to compare the two groups on all items collected, using t-test and Mann-Whitney U tests as appropriate with two-tailed testing (i.e. accepting that harm is also possible). The expectation is that the intervention group will have:

- Better sleep on the questionnaire
- Less use of night sedation over their hospital stay
- Less falls over their hospital stay
- A shorter length of stay

Secondary analyses will investigate:

- Variation between wards on all measures, irrespective of patient group.
- Reported use of and problems with the earplugs and eye masks.

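### Section 9.1 waives recording of all events except falls and deaths, with no exception for aid-related ones; this conflicts with 9.2 and leaves non-fall aid-related harm without systematic capture

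*Combined protocol and SAP*

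**What the plan says.** Section 9.1 defines a serious adverse event, notes that patients are expected to have many events, and continues: "With the exception of falls and deaths these will" not "be recorded because the likelihood of the intervention causing serious harm is considered very small". Burden of collection is its second reason. The waiver does not separate serious from minor events, or events caused by the aids from unrelated illness.

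Section 9.2 sets four duties:
- a report to the ethics committee of SAEs that the Chief Investigator judges related and unexpected: "Reports of related and unexpected SAEs should be submitted within 15 working days" of the Chief Investigator becoming aware;
- a 24-hour report to the study team: "All SAEs (other than those defined in the protocol as not requiring reporting) must be reported";
- an immediate report to the R&D office of any SAE that is identified;
- a form: "All SAE information must be recorded on an SAE form".

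Section 3, under Risks to participants, names harms that the aids might cause. They include allergy ("Risk of patient or staff having an allergic reaction to the product"), swallowing or choking, infection (including "increasing risk of patients getting otitis externa (outer ear infections"), pressure ulcer, and confusion with falls.

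Sections 7.6, 7.7, 10.1 and 10.3 determine what reaches the analysis. The post-discharge extraction in 7.6 includes falls and none of the other named harms. Section 7.7 lists an adverse event from the intervention as a ground for discontinuation and has the reason recorded. Section 10.1 plans a secondary analysis of reported problems with the aids. Section 10.3 leaves out participants who withdrew consent or did not complete the questionnaire.

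**The concern.** Two parts of the safety section give different instructions. Someone following 9.1 would write down nothing but falls and deaths. Someone following 9.2 would complete a form for every SAE. If the 9.2 carve-out is meant to point back to 9.1, the exemption reaches even a serious event caused by an earplug. If it is not, the two sections contradict each other.

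The reasons in 9.1 also do not cover everything that it waives. A very small chance of serious harm is no reason to leave out non-serious harm from the aids. The burden argument fits unrelated inpatient illness well, but fits a handful of aid-specific events poorly.

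At stake is whether the trial can describe the harms that its own risk assessment foresaw. The aids are simple and are given to people who may use them with little supervision, so the rate of ear, skin and airway problems is something a ward would want to know before adopting them.

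**Working it through.** The documents state no safety figure to reproduce. The check is mainly a comparison of passages, followed by one calculation for scale.

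**Step 1: does the carve-out reconcile 9.1 and 9.2?** The parenthesis in 9.2 exempts SAEs that the protocol defines as not requiring reporting. Section 9.1 is about recording and does not present itself as that list.
- If 9.1 is the list, nearly every SAE except death is exempt from the 24-hour report, including one caused by the aids. The ethics committee, R&D and form duties carry no such exemption, so a conflict remains.
- If 9.1 is not the list, the 24-hour duty covers events that 9.1 says will not be recorded.

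Neither reading makes the two sections agree.

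**Step 2: where would each named harm be recorded?** Scores are from section 3 (likelihood × severity).

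| Harm | Score | In the 7.6 extraction? | Other route |
|---|---|---|---|
| Infection, including outer ear | 3 × 2 = 6 | No | Partial |
| Confusion/falls | 2 × 3 = 6 | Falls yes, confusion no | Falls compared by arm (10.1) |
| Allergy | 1 × 4 = 4 | No | Partial; named in 7.7 |
| Swallowing or choking | 1 × 4 = 4 | No | Partial |
| Pressure ulcer | 1 × 3 = 3 | No | Partial |

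Infection has the highest likelihood in the list and shares the highest score. The other risk scoring 6 is the one whose main consequence, falls, is collected.

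**Step 3: how far do the partial routes reach?**
- Section 7.7 works only if the participant withdraws or is withdrawn. The reason is not among the 7.6 items and has no planned analysis. Anyone who withdraws consent leaves the analysis under 10.3.
- Section 10.1 does not say how problems are asked about or which ones. If the questionnaire is the source, it is given once, more than one day after recruitment. A later harm that does not lead to withdrawal then has no route.
- Section 7.2 treats an unfilled questionnaire as refusal of consent for the use of that data, section 6.2 rules out collecting data from those unable to consent at that point, and 10.3 excludes non-completers. A patient who becomes confused or too ill to complete it may therefore be missing from the harm data.

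**Step 4: scale.** Inputs: 400 participants (10.2) and an equal chance of each allocation (7.4), so 400 × 0.5 = 200 expected on the intervention. Assume that every event among them is captured.
- Zero events observed, one-sided 95% upper bound: 1 − 0.05^(1/200) = 0.0149, about 1.5%.
- Chance of seeing at least one event at true risk r: 1 − (1 − r)^200. For assumed r of 0.1%, 0.5%, 1% and 2% this gives 18%, 63%, 87% and 98%.

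The values of r are assumptions; the documents give none.

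**The case against.** The strongest reply is that 9.1 is a proportionate waiver. It follows directly on the remark that patients will have many events, so it can be read as covering the expected illness of inpatients and not events caused by the aids. Section 3 scores all its risks as low. That reading is reasonable, but the text does not state it, and ward staff should not have to infer it. The proportionality argument stands for unrelated illness, and the fix keeps it.

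Four stronger conclusions are tempting, and the documents do not support them.
- A reader might infer that harm from the aids will go unseen. Section 7.7 records the reason when such an event leads to discontinuation, 10.1 analyses reported problems, and falls are compared by arm.
- A reader might infer that the Chief Investigator cannot judge relatedness. The time limits in 9.2 run from awareness, not from an entry on a data form, so the judgement is possible. What is weak is ascertainment.
- A reader might infer that 9.2 certainly removes aid-related events from reporting. Its carve-out qualifies only the 24-hour report, and 9.1 does not claim to define it.
- A reader might infer that the trial will declare the aids harmless. No such conclusion is planned. The phrase "accepting that harm is also possible" in 10.1 explains two-tailed testing of the items that are collected, where an effect in the harmful direction is measured.

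It is also fair to say that the questionnaire's content is not in the documents, so how well it asks about problems cannot be checked.

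**Conclusion.** The point holds in a limited form. Sections 9.1 and 9.2 are inconsistent about what is recorded, and 9.1 has no exception for events related to the aids. Non-fall harms named in section 3 have no systematic collection by arm, only routes that depend on withdrawal or on a reported problem.

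The amount of harm data lost cannot be estimated, because the documents give neither event rates nor uptake of the aids. The 1.5% bound indicates what full capture in about 200 patients could support; it does not measure the defect. It rests on an expected arm size under simple randomisation and on complete ascertainment. This is a worthwhile, inexpensive improvement to the safety data and does not threaten the primary comparison.

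**What to change.** 1. In 9.1, limit the exemption to events not attributed to the earplugs or eye mask.
2. In 9.2, say which events the carve-out covers, and state that any serious event possibly caused by the aids is recorded and sent to the Chief Investigator.
3. Add a short checklist of the section 3 harms: ear infection, allergic reaction, swallowed or inhaled earplug, pressure ulcer. Word it so that it applies to both arms: event present or absent, with attribution to the aids recorded separately in the intervention arm. Complete it at the questionnaire visit and again at the post-discharge extraction, within the consent limits in 6.2 and 7.2, and report it by arm.
4. Tabulate the 7.7 withdrawal reasons alongside it.

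The cost is a little form-filling and some extra review of up to 400 sets of notes, at contacts that already take place. The verbal explanation in 7.2 lists only falls, sleeping tablets and length of stay as routine data, so the added items should be named there. The change does not recover data from people who decline or cannot complete the questionnaire; their number by arm should be reported next to the checklist results.

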#### 9.2. Reporting Procedures for Serious Adverse Events

A serious adverse event (SAE) occurring to a participant should be reported to the REC that gave a favourable opinion of the study where in the opinion of the Chief Investigator the event was 'related' (resulted from administration of any of the research procedures) and 'unexpected' in relation to those procedures. Reports of related and unexpected SAEs should be submitted within 15 working days of the Chief Investigator becoming aware of the event, using the HRA report of serious adverse event form (see HRA website).

All SAEs (other than those defined in the protocol as not requiring reporting) must be reported on the Oxford University Hospitals NHS Trust SAE reporting form to OUH study team within 24 hours of the Site Study Team becoming aware of the event by email or fax.

In the unlikely event that a Serious Adverse Event is identified, it will be reported to the R&D office immediately. SAE reports should be faxed or emailed to: [name] or [contact]

All SAE information must be recorded on an SAE form and faxed, or scanned and emailed, to R&D. Additional and further requested information (follow-up or corrections to the original case) will be detailed on a new SAE Report Form and faxed/emailed to R&D.

#### **10. STATISTICS AND ANALYSIS**

All data will be entered onto a secure computer database, with no patient-identifiable data. The patient registration number given will be used.

# **10.1.** Description of Statistical Methods

There will be no interim analysis.

The primary analyses will be to compare the two groups on all items collected, using t-test and Mann-Whitney U tests as appropriate with two-tailed testing (i.e. accepting that harm is also possible). The expectation is that the intervention group will have:

- Better sleep on the questionnaire
- Less use of night sedation over their hospital stay
- Less falls over their hospital stay
- A shorter length of stay

Secondary analyses will investigate:

- Variation between wards on all measures, irrespective of patient group.
- Reported use of and problems with the earplugs and eye masks.

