### 1. SYNOPSIS

Study Title	SleepSure: a randomised controlled trial to assess the effects of eye masks and earplugs on the quality of sleep for patients in hospital.			
Internal ref. no. / short title	SleepSure: a study aimed at improving sleep for hospital inpatients			
Study Design	Randomised Controlled Trial			
Study Participants	Patients admitted to adult general medical and surgical wards at Oxford University Hospitals NHS Foundation Trust			
Planned Sample Size	400			
Planned Study Period	01 February 2016- 31 January 2017 Pilot data collection 01 February 2016 to 14 February 2015 Recruitment 01 March 2016 – 31 May 2016 (last follow-up 14 June 2016)			
	Objectives	Outcome Measures		
Primary	Do earplugs and eye masks help hospital patients to sleep better?	SleepSure Questionnaire, based on the validated Richards-Campbell Sleep Questionnaire		
Secondary	Does the use of earplugs and eye masks lead to a reduced length of stay, reduced incidence of falls or reduced use of sleep aid medication? How many patients provided with earplugs and an eye mask choose to use them?	Length of stay (days) Number of falls recorded during stay Doses of zopiclone (sleeping tablet) used to help sleep during stay Use of earplugs and eye masks (SleepSure sleep questionnaire)		

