#### The question

Our question is simple: Does the provision of earplugs and eye masks improve the sleep of hospital inpatients?

Secondary questions are whether this provision leads to a reduced length of stay, reduced incidence of falls and reduced use of sleep aid medication. We also wish to discover how many patients provided with earplugs and an eye mask choose to use them.

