### 4. OBJECTIVES AND OUTCOME MEASURES

Objectives	Outcome Measures	Timepoint(s) of evaluation of this outcome measure (if applicable)
Primary Objective Do ear plugs and eyemasks improve inpatient experience of sleep?	SleepSure sleep questionnaire	Questionnaire given >1 day after recruitment
Secondary Objectives A) How many patients provided with eye masks and earplugs choose to use them?	SleepSure sleep questionnaire	Questionnaire given >1 day after recruitment
B) Does the use of earplugs and eye masks lead to reduced length of stay?	Length of stay data from hospital administration system	After discharge
C) Does the use of earplugs and eye masks lead to reduced use of sleep aid medication?	Drug chart data from electronic records.	After discharge
D) Does the use of earplugs and eye masks lead to a reduced incidence of falls?	Falls data from centrally collated routinely collected information	After discharge

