#### 7.6. Subsequent Visits

At the final visit (>1 day after recruitment) the SleepSure research nurse will provide a SleepSure Questionnaire. After discharge the participant's anonymised ID number, age, gender, date of admission, date of discharge, length of stay, number of falls, doses used of zopiclone will be extracted from the notes and recorded by the SleepSure research nurse onto an Excel spreadsheet stored in a secure location on the Trust network with access only via a password-protected computer. The results of the SleepSure questionnaire will also be recorded onto this secure document at this time. (Please see section 11 for more information.)

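### Section 10.1 groups sleep, night sedation, falls and length of stay under the primary analyses, although the objectives make sleep the only primary question

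*Combined protocol and SAP*

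**What the plan says.** Section 10.1 states: "The primary analyses will be to compare the two groups on all items collected, using t-test and Mann-Whitney U tests as appropriate". The tests are two-sided, so that a harmful effect could also be detected. Directly beneath is a list of what the intervention group is expected to show, in which sleep, night sedation, falls and length of stay have equal standing. The section then gives its own list of secondary analyses, which has two entries: variation between wards regardless of arm, and "Reported use of and problems with the earplugs and eye masks".

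Three other places rank the outcomes differently:

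- The Synopsis has sleep in its primary row. Its secondary row asks whether the aids "lead to a reduced length of stay, reduced incidence of falls or reduced use of sleep aid medication".
- Section 3, under the heading for the question, poses sleep as the study question and continues: "Secondary questions are whether this provision leads to a reduced length of stay, reduced incidence of falls and reduced use of sleep aid medication".
- Section 4 has a single primary objective, "Do ear plugs and eyemasks improve inpatient experience of sleep". The secondary objectives include "Does the use of earplugs and eye masks lead to reduced length of stay", with sleep medication and falls as separate entries.

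Section 7.6 lists what is extracted after discharge, including "age, gender, date of admission, date of discharge, length of stay, number of falls, doses used of zopiclone". No section gives an alpha, a multiplicity rule, or a statement of which section prevails if they differ.

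**The concern.** The analysis section should carry the ranking of outcomes through to the tests. Here it does not. Three outcomes that are secondary in the Synopsis, section 3 and section 4 sit under the primary label in 10.1, and they are absent from the list that 10.1 itself calls secondary.

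What is at stake is the status of the trial's claim. Suppose sleep shows no difference but length of stay is significantly shorter. Under the objectives, that is a negative primary result with a secondary observation. Someone quoting 10.1 could present it as a positive primary result. With several outcomes under one label and no rule for combining them, the chance of at least one false-positive finding also exceeds that of a single test.

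**Working it through.** **Step 1: compare the sections.**

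| Outcome | Synopsis | Section 3 | Section 4 | Section 10.1 |
|---|---|---|---|---|
| Sleep | Primary | Main question | Primary | Primary analyses |
| Length of stay | Secondary | Secondary | Secondary | Primary analyses |
| Falls | Secondary | Secondary | Secondary | Primary analyses |
| Sleep medication | Secondary | Secondary | Secondary | Primary analyses |
| Use of the aids | Secondary | Listed with the secondary questions | Secondary | Secondary analyses |

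The labels disagree on three outcomes and agree on sleep and on use of the aids. This comparison establishes the point, and no arithmetic is needed for it.

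**Step 2: illustrate the size.** The plan has no error-rate figure to reproduce. Assumptions that are not in the document: two-sided 5% per test, the four outcomes listed in 10.1, normal test statistics with one common correlation r, and no true effect on any outcome.

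With independent outcomes (r = 0):

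- At least one significant in either direction: 1 − 0.95⁴ = 0.1855.
- At least one significant in the favourable direction (2.5% each): 1 − 0.975⁴ = 0.0963.
- Sleep not significant, but at least one of the other three significantly better: 0.95 × (1 − 0.975³) = 0.95 × 0.0731 = 0.0695 (0.06948 before rounding, so 6.9%).

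For r > 0, write each statistic as √r·U + √(1−r)·Eⱼ, with U and the Eⱼ independent standard normal. Given U the statistics are independent, so the same products apply and are averaged over U by numerical integration.

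| Event | r = 0 | r = 0.5 | r = 0.9 | One test alone |
|---|---|---|---|---|
| At least one of four significant, either direction | 18.5% | 15.6% | 9.4% | 5% |
| At least one of four significantly better | 9.6% | 7.8% | 4.7% | 2.5% |
| Sleep not significant, at least one of the other three significantly better | 6.9% | 5.3% | 2.2% | cannot occur |

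The third row matches the harm described above, because only a favourable secondary result would be attractive to promote. If direction is ignored, the third-row event has probability 18.5% − 5% = 13.5% at r = 0, about twice the favourable figure.

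Four is the number of outcomes that 10.1 lists. If single questionnaire items also count as items collected, there are more tests, but the document does not set those items out and the number cannot be fixed.

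**The case against.** The strongest reply is that 10.1 sorts types of analysis and does not rank outcomes. On this reading, the primary analyses are the randomised comparisons between arms. The secondary analyses are those that are not between-arm comparisons, namely ward variation and experience with the aids. The wording supports this: taken literally, the items collected include age, gender and admission date (section 7.6), which nobody would treat as primary outcomes. The ranking itself is stated three times, consistently, elsewhere.

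Much of this stands. The reading is plausible, and the objectives are the natural guide. It does not remove the conflict, because nothing in section 10 gives that meaning or marks sleep as the one primary test. For use of the aids, moreover, the secondary label in 10.1 coincides with that in the objectives, so a reader could fairly take the label to mean the same thing in both places.

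Two stronger readings are tempting and are not supported. A reader might infer that 10.1 overrides the objectives and makes length of stay, falls and medication co-primary; no section says so, and reporting the trial that way would openly contradict the Synopsis and section 4. A reader might also take 18.5% as the trial's false-positive rate. That figure needs an alpha the document does not state, independent outcomes, and counting of harmful as well as favourable results. The missing alpha is a separate omission and is no evidence for the conflict.

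**Conclusion.** The concern holds as an inconsistency: on the primary label, section 10.1 is wrong as written when set against the ranking given three times elsewhere. The consequence is less certain than the inconsistency. The plan leaves room to present a secondary result as primary; it does not authorise doing so.

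Under the stated assumptions, the chance of the specific misleading outcome (sleep not significant, something else significantly better) is roughly 2% to 7% across correlations from 0.9 to 0. The conflict between sections does not depend on these figures. It should be corrected because the repair costs little and restores a single primary claim.

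**What to change.** In section 10.1:

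- State that the primary analysis compares the two groups on one sleep score from the SleepSure questionnaire, with one test and one two-sided alpha. The sponsor should name all three before the data are analysed. Leaving the choice between t-test and Mann-Whitney open for this comparison would mean that it is not pre-specified.
- State that the between-arm comparisons on length of stay, zopiclone doses, falls and any other questionnaire items are secondary, two-tailed, using t-test or Mann-Whitney U as appropriate.
- In the list of expectations, mark sleep as primary and the other three as secondary.
- Leave the ward-variation analysis and the analysis of use of and problems with the aids as they are.

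Once one score and one test are fixed, the primary claim needs no multiplicity adjustment.

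The cost is a rewording of the opening sentence and the list, plus three decisions for the sponsor (score, test and alpha). Design, data collection and sample size are untouched. The downside is that a positive result on length of stay, falls or medication can no longer be presented as a primary finding.

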# 7.4. Randomisation, blinding and code-breaking

Every patient recruited will first be registered by the SleepSure research nurse onto an electronic password-protected Participant ID log in a secure location on the Trust network. This will generate a trial number (e.g. WPH WdA 007 [hospital, ward, number]).

Randomisation:

Using a random number generator performing simple randomisation opaque numbered envelopes will be filled with a piece of paper stating control or intervention with an equal chance of each individual envelope containing a control or an intervention instruction. 50 sealed envelopes will be stacked into a box on each ward, each with a unique identifier number on the outside. When a potential participant is identified the SleepSure research nurse will go to the next envelope in the box and open it to determine if the patient is in the control or intervention arm.

If the patient is allocated to the trial arm, the research nurse will give the patient a set of earplugs and an eyeshade, and explain their use, checking that the patient can use and remove them safely giving instruction as required. The earplugs and eye mask will then be placed into a transparent plastic wallet, labelled with the patient's name, the study and placed within easy reach of the patient.

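### Cheap improvement, not an error: age, gender and ward at registration could be prespecified as covariates in the SleepSure comparison once its score is defined

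*Combined protocol and SAP*

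**What the plan says.** **Test.** Section 10.1 states: "The primary analyses will be to compare the two groups on all items collected, using t-test and Mann-Whitney U tests as appropriate". Testing is two-tailed and no covariate is named. Ward appears only in a secondary analysis: "Variation between wards on all measures, irrespective of patient group".

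**Allocation.** Section 7.4 describes simple randomisation, "with an equal chance of each individual envelope containing a control or an intervention instruction". It adds that "50 sealed envelopes will be stacked into a box on each ward". Neither section 5 nor section 7.4 mentions stratification or blocking.

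**Ward.** Section 7.4 says "Every patient recruited will first be registered by the SleepSure research nurse onto an electronic password-protected Participant ID log", and of that step: "This will generate a trial number (e.g. WPH WdA 007 [hospital, ward, number" (the bracket closes after the last word). Registration comes before the envelope is opened. For the database, section 10 says: "The patient registration number given will be used".

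**Age and gender.** Section 7.6 lists the data taken after discharge: "age, gender, date of admission, date of discharge, length of stay, number of falls, doses used of zopiclone will be extracted from the notes". Under section 6.2, no data are collected from people who cannot consent when the questionnaire is completed.

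**What is absent.** Section 7.5 plans no baseline measure beyond eligibility. Section 10.2 gives 400 as a recruitment estimate without a calculation. The synopsis names the instrument on which the questionnaire is based, but the supplied text gives no scoring rule.

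**The concern.** In an unadjusted comparison, any variation in the score that ward, age or gender explains stays in the standard error. The plan already records, or lets one infer, all three, and none can be altered by allocation. It examines ward only with the arms pooled, which does nothing for the arm comparison.

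What is at stake is precision. The sample of 400 has no power calculation behind it, and section 10.3 drops participants without a questionnaire, so fewer may be analysed. Timing also matters: covariates added after the arms have been compared would look data-driven.

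**Working it through.** **Plan's own figure.** The 400 cannot be reproduced, because no alpha, power, SD or effect size is given.

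**Inputs from the documents.** N = 400 (section 10.2), 10 wards (section 5), simple randomisation (sections 5 and 7.4), two-sided test (section 10.1).

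**Assumed, not in the documents.** Alpha 0.05, true difference 0.25 SD, normal score, and R2 of 0 to 0.20. N is 400, or 320 if 20% return no questionnaire (400 × 0.80).

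**Step 1: is the unadjusted test undermined by the lack of covariates?** Each envelope has its own equal chance of either arm. A box of 50 is therefore not a balanced block, and ward is not a stratification factor that the model must carry. In simulations with 10 wards of 40, at nominal 5%, type I error was 4.5 to 5.0% for the t-test and 4.5 to 5.1% for a model with age, gender and ward. Ward, age and gender jointly explained 0%, 10% or 20% of the variance. So omitting them does not inflate type I error.

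**Step 2: formula for power.** With k covariate terms:

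SE = SD × sqrt[(1 − R2) × (4/N) × (N − 2)/(N − 2 − k)], with power from the noncentral t on N − 2 − k degrees of freedom.

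- Unadjusted, N = 400: SE = sqrt(4/400) = 0.100 SD, noncentrality 0.25/0.100 = 2.50, power 70.3%.
- Unadjusted, N = 320: SE = sqrt(4/320) = 0.1118 SD, noncentrality 2.236, power 60.6%.
- Ward as nine fixed terms plus age and gender (k = 11), N = 400, R2 = 0.10: SE = sqrt(0.90 × 0.01 × 398/387) = 0.0962 SD, noncentrality 2.599, power 73.6%.

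**Step 3: power with ward as nine fixed terms plus age and gender.**

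| N | Unadjusted | R2 0 | R2 0.05 | R2 0.10 | R2 0.20 | Break-even R2 |
|---|---|---|---|---|---|---|
| 400 | 70.3% | 69.1% | 71.3% | 73.6% | 78.5% | 0.028 |
| 320 | 60.6% | 59.1% | 61.3% | 63.6% | 68.7% | 0.035 |

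If the covariates explain nothing, the loss is 70.3 − 69.1 = 1.2 points, or 60.6 − 59.1 = 1.5 points.

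**Step 4: age and gender alone (k = 2).** At R2 0, the loss is 70.3 − 70.1 = 0.2 points (N = 400) or about 0.3 points (N = 320). Break-even R2 is 0.005 and 0.006. Here R2 is what age and gender explain by themselves.

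**Step 5: ward as a random intercept, with age and gender.** Simulated power (20,000 runs, even wards, REML, t with N − 4 degrees of freedom, two thirds of R2 from ward), unadjusted v adjusted:

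| N | R2 0 | R2 0.05 | R2 0.10 | R2 0.20 |
|---|---|---|---|---|
| 400 | 70.4 v 70.3% | 70.5 v 71.7% | 70.6 v 73.7% | 71.0 v 78.8% |
| 320 | 60.9 v 60.7% | 60.6 v 61.8% | 60.5 v 63.7% | 61.5 v 69.6% |

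The Monte Carlo standard error is about 0.3 points for each power figure. The loss at R2 0 is 0.1 to 0.2 points, and the gain is 1.2 points at R2 0.05 and 3.1 to 3.2 at R2 0.10. With 400 patients in uneven wards (20 to 50 each), every figure was within 0.2 points of the even-ward result. Type I error was 4.7 to 5.3% for both analyses.

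**The case against.** The strongest case against raising this is that it is a preference. The plan promises no adjustment, the design does not require it, and the benefit rests entirely on assumed values. With no baseline sleep score, an obvious prognostic covariate is missing, so R2 may be small. With fixed ward terms and R2 below about 0.03, power falls. All of this stands, and it is why the point is a suggestion and not an error.

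It is also fair that nothing can be adopted until the SleepSure score is defined, and that other matters rank higher: the score itself, the exclusion of non-completers, and treating every item as primary. A mixed model also needs a degrees-of-freedom method and a rule for zero ward variance; the fix supplies both.

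Three stronger readings are tempting, and the documents support none of them.

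- *That boxing envelopes by ward makes ward a stratification factor the analysis wrongly ignores.* Sections 5 and 7.4 describe simple randomisation only.
- *That the unadjusted comparison is therefore sound as a whole.* The check covers only the omission of covariates. It does not clear the completer-only rule in section 10.3, in a trial whose participants know their allocation, or the open choice of test and the multiple primary items in section 10.1. As an illustration, take no true effect and roughly 80% completion. When completion depended on sleep in one arm only (logit slope 0.5 or 1.0 per SD), the bias was 0.10 or 0.20 SD and the false-positive rate 15% or 45%. Adjusting for age, gender and ward would not be expected to remove that bias.
- *That a gain of about 8 points is in prospect.* That needs R2 0.20, which nothing in the documents supports. Nor do they say that wards are expected to differ in sleep.

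**Conclusion.** This holds as a cheap, optional improvement. Under simple randomisation, leaving covariates out of the arm comparison is not in itself a fault; what the plan forgoes is possible precision from variables it already has.

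Under the assumed 0.25 SD effect, the gain is about 1 power point at R2 0.05 and about 3 at R2 0.10, and it could be near zero. The worst-case loss is small unless ward is fitted as fixed terms.

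Two factual limits apply. That ward will be in the analysis file is an inference from the example trial number in section 7.4 and the use of the registration number in section 10; the extraction list in section 7.6 does not name it. Age and gender are available only for participants whose data are collected. They are extracted after discharge, but allocation cannot change them, so they remain legitimate covariates.

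**What to change.** First define the SleepSure score. If it supports a mean difference, add to section 10.1, before any analysis by arm, wording such as:

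*The primary analysis will estimate the difference in mean SleepSure score between allocated arms, with 95% CI, from a linear mixed model (REML) adjusted for age (continuous), gender and ward at registration (random intercept), with [named method] degrees of freedom. If the ward variance is estimated as zero, the ward term will be dropped. The unadjusted t-test on the same score will be a sensitivity analysis.*

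The minimal option is a linear model with age and gender alone. Whichever is chosen, confirm that ward at registration is held in the analysis file, and use that value for patients who later move. If the team prefers an unadjusted primary analysis, it should say that this is deliberate. If the score does not support a mean difference, this wording does not apply.

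The cost is analysis wording only, with no new data collection. The price in power if the covariates explain nothing is 0.1 to 0.2 points (random intercept, simulated), 0.2 to 0.3 (age and gender alone) or 1.2 to 1.5 (nine fixed ward terms).
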